**Figure 5: Path for Subjects with Two Indeterminate Interferon-Gamma Release Assay Results at Screening**

IGRA = interferon-gamma release assay; TB = tuberculosis

### **8.7.3 Clinical Safety Laboratory Assessments**

The central laboratory will perform safety laboratory assessments (except urine pregnancy tests ( [REDACTED] ) and provide reference ranges with laboratory reports. Investigators must document their review of each laboratory safety report. A laboratory test result that the investigator considers clinically relevant for safety is to be recorded on the eCRF, if applicable. Results of [REDACTED] [REDACTED] clinical laboratory tests performed during the screening period must be reviewed before the subject is allowed to proceed in the study.

#### **8.7.3.1 Screening Laboratory Assessments**

- Chemistry, hematology, coagulation, immunohematology:
  - Metabolic chemistry panel: glucose, blood urea nitrogen (BUN), creatinine (and eGFR using the MDRD equation), sodium, potassium, chloride, carbon dioxide, calcium, phosphate, total protein, albumin, uric acid, total bilirubin, direct bilirubin, phosphorus, magnesium, gamma glutamyltransferase (GGT), ALP, ALT, AST, CK, lactate dehydrogenase (LD), and amylase
  - TSH; if abnormal, a T4 will also be done
  - Follicle-stimulating hormone (FSH) for WOCBP if needed to confirm postmenopausal status (see [APPENDIX 4](#))
  - hsCRP
  - Quantitative immunoglobulins (Igs): IgA, IgG, and IgM
  - Trough MPA concentration (for subjects already taking MMF at screening)
  - CBC: white blood cell (WBC) count, RBC count, hemoglobin, hematocrit, RBC indices, platelet count, and an automated differential; a manual WBC differential will be performed if indicated
  - Coagulation: prothrombin time, International Normalized Ratio, and partial thromboplastin time
  - Direct antiglobulin test (Coombs test) (screening only; thereafter, as needed per investigator)
- Urine:
  - Urinalysis with microscopic examination (if the urinalysis is positive for leukocytes, blood, or bacteria, a urine culture should be performed if appropriate)

- UPCR assessed using a first morning (or second if the first was not collected) voided urine specimen, and a 24-hour urine specimen
- Urine pregnancy test (WOCBP only)
- Screening serology: HBsAg, anti-HBs, anti-HBc; HBV DNA if needed; anti-HCV and HCV DNA if needed; anti-HIV-1, anti-HIV-2
- IGRA for TB screening
- ANA
- [REDACTED]
- APAs: (aCL, LA, and anti-β2GP1)
- [REDACTED]
- [REDACTED]
  - [REDACTED]
  - [REDACTED]
  - [REDACTED]

### 8.7.3.2 Clinical Safety Laboratory Assessments During the Study

A central laboratory will perform safety laboratory assessments (except urine pregnancy tests [REDACTED] [REDACTED]s) and provide reference ranges with the results. Investigators must document their review of each laboratory safety report. Clinically relevant laboratory results (as determined by the investigator) will be recorded on the appropriate AE page of the eCRF ([Section 8.5](#)).

See [Section 6.1](#) for information on additional pregnancy testing for WOCBP who initiate the drug in Part A, and [Section 6.2](#) for more information about frequency of CBCs during the first few months of MMF treatment.

Results of clinical laboratory tests performed during screening must be reviewed before the first dose of blinded study treatment. Laboratory assessments for the study include the following:

- Hematology: WBC count, RBC count, hemoglobin, hematocrit, RBC indices, platelet count, and an automated differential; a manual WBC differential will be performed if indicated
- Metabolic chemistry panel: glucose, BUN, creatinine (and eGFR using the MDRD equation), sodium, potassium, chloride, carbon dioxide, calcium, phosphate, total protein, albumin, uric acid, total bilirubin, direct bilirubin, phosphorus, magnesium, GGT, ALP, ALT, AST, CK, LD, and amylase
- Urinalysis and microscopic examination of sediment (clean-catch sample); if the urinalysis is positive for leukocytes, blood, or bacteria, a urine culture should be performed if appropriate

- UPCR
  - Visit A4, Visit B7, and Visit B14: Two 24-hour urine specimens will be collected; if a third 24-hour urine specimen is needed, this should be collected as soon as possible but no more than 10 days after the results of the first two specimens are reported; see [Section 8.4.1](#) for more details (the exception is for subjects with 12 weeks of MMF at a dose of 1.5 to 3.0 g/day at the time of screening, who will collect a single 24-hour urine specimen for Visit A4)
  - All visits in Part A, Part B [REDACTED]: First morning voided urine specimens will be collected; the first morning void is preferred; however, if the first morning void was not collected, the second morning void will be used
  - [REDACTED]

#### **8.7.4 Body Weight and Vital Signs**

[figure not shown]
Body weight, blood pressure, heart rate, respiratory rate, and temperature will be recorded. Blood pressure and heart rate should be measured after the subject has been resting quietly for at least 5 minutes. At screening, the blood pressure will be measured twice, at least 5 minutes apart, and the average will be used for the eligibility assessment.

[figure not shown]
#### **8.7.5 Electrocardiograms**

[figure not shown]
A single 12-lead ECG will be recorded after the subject has been supine for at least 5 minutes.

[figure not shown]
#### **8.7.6 Renal Biopsy**

[figure not shown]
Renal biopsies performed during the study will be processed and analyzed by a central pathology laboratory. The change from the biopsy results assessed at screening to the (optional) biopsies after 52 [REDACTED] weeks (and/or early discontinuation, if discontinuation occurs after Week 24) of blinded study treatment will be evaluated for LN Class, National Institutes of Health (NIH) Chronicity Index, and NIH Activity Index. [REDACTED]

[figure not shown]

## **9 STATISTICAL CONSIDERATIONS**

### **9.1 Sample Size Determination**

A sample size of 52 randomized subjects in the combined BMS-986165 treatment groups (26 subjects in the BMS-986165 6 mg BID group and 26 in the BMS-986165 3 mg BID group) and 26 subjects in the placebo group will provide 88% power (at a one-sided significance level of 0.10)

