**Statistical Methods:**

A sample size of 52 randomized subjects in the combined BMS-986165 treatment groups (26 subjects in the BMS-986165 6 mg BID group and 26 in the BMS-986165 3 mg BID group) and 26 subjects in the placebo group will provide 88% power (at a one-sided significance level of 0.10)

The change from baseline in log-transformed 24-hour UPCR at Week 24 will be analyzed using analysis of covariance (ANCOVA) with treatment groups and randomization stratification factors as fixed effects and the log-transformed baseline value as a covariate added in the model. Relative treatment differences on least-square means and corresponding 2-sided 95% CIs in primary endpoint, the percentage change from baseline in 24-hour UPCR at Week 24 on the original scale, will be provided for combined BMS-986165 treatment groups and placebo. Additionally, least-square means and 2-sided CIs will be provided for the relative difference between each BMS-986165 treatment group and placebo will be provided in similar method for the Full Analysis Set (FAS). There will be no adjustment of the Type 1 error rate for multiple comparisons or testing of multiple endpoints.

Treatment-emergent adverse events (TEAEs), serious adverse events, deaths, adverse events (AEs) leading to discontinuation of the investigational product (IP), AEs by maximum severity, and AEs by relationship to IP will be summarized by the Medical Dictionary for Regulatory Activities

system organ class and preferred term. All TEAEs, AEs of interest, as well as any adjudicated AE category will also be summarized by preferred term sorted by decreasing frequency.

[REDACTED]

[figure not shown]
An external Data Monitoring Committee will perform safety monitoring by blinded treatment group.

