  - Approximately 1 week between the last visit in Part A (Visit A4) and the first visit in Part B (Visit B1)
  - Part B: Randomization followed by blinded study treatment for 52 weeks plus continued open-label MMF with or without corticosteroids (or just continued open-label MMF with or without corticosteroids for those who are not randomized); all subjects will attend study visits every 4 weeks and undergo assessments as indicated in [Table 3](#)
  - [REDACTED]
- A follow-up period of  $28 \pm 3$  days followed by an end-of-study visit

After a screening period of up to 28 days, eligible subjects will enter Part A of the study, an open-label MMF run-in period of up to 12 weeks. Subjects may continue taking MMF as previously prescribed (if at a dose of 1.5 to 3.0 g/day) until they reach 12 weeks of treatment or, if not receiving MMF or previously prescribed < 1.5 g/day, subjects will be either started on MMF when they enter Part A or titrated to a dose of 1.5 to 3.0 g/day for the full 12 weeks of Part A. Subjects who have been taking MMF at a dose of 1.5 to 3.0 g/day for  $\geq$  12 but  $\leq$  24 weeks at the time of screening will promptly be evaluated for continuation in Part B and for randomization. The suggested target dose of MMF at the first visit in Part B is 1.5 to 2.0 g/day (maximum 3.0 g/day) unless limited by intolerance or toxicity (refer to [Section 6.1](#) for further details regarding individual target dose).

After at least 12 weeks of open-label MMF treatment of at least 1.5 g/day (either only during Part A of the study or including previously prescribed MMF before and during screening), subjects

will be assessed to determine whether they meet the criteria to continue in Part B (see [Section 4.1.2.1](#)), and whether they meet the randomization criteria (see [Section 4.1.2.2](#)). Those subjects who meet all the criteria to continue in Part B and meet the randomization criteria will be assigned in a double-blind manner (1:1:1) to one of the following treatment groups:

- BMS-986165 3 mg BID + continued open-label MMF with or without corticosteroids
- BMS-986165 6 mg BID + continued open-label MMF with or without corticosteroids
- Placebo BID + continued open-label MMF with or without corticosteroids

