### **4.2 Number of Subjects**

A sufficient number of individuals will be screened so that approximately 78 subjects will be randomized in Part B of the study (52 subjects in the combined BMS-986165 groups and 26 subjects in the placebo group).

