### 9.4.1 Primary Endpoint Analysis

The analysis of covariance (ANCOVA) for change from baseline in log-transformed 24-hour UPCR at Week 24 will be performed with treatment groups (BMS-986165 3 mg BID, BMS-986165 6 mg BID, and placebo) and randomization stratification factors (24-hour UPCR < 3.0 mg/mg versus  $\geq$  3.0 mg/mg, and total cumulative IV corticosteroid methylprednisolone < 250 mg versus  $\geq$  250 mg) as fixed effects with log-transformed baseline value added into the model as a covariate. Relative treatment differences in percentage change from baseline in 24-hour UPCR at Week 24 on the original scale based on least-square means and the corresponding 2-sided 95% CIs will be provided for combined BMS-986165 treatment groups and placebo. Additionally, least-square means and 2-sided 95% CIs will be provided for the relative difference between each BMS-986165 treatment group and placebo for the FAS.

Prior to unblinding the appropriateness of the log-transformation will be investigated. Further details will be provided in the SAP. For statistical testing, comparison of the combined BMS-986165 treatment group compared to placebo will be performed. There will be no adjustment of the Type 1 error rate for multiple comparisons or testing of multiple endpoints.

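### Does testing the primary comparison at one-sided 0.10 while reporting a two-sided 95% CI leave the primary result ambiguous?

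*Combined protocol and SAP*

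**What the plan says.** The synopsis (Statistical Methods) and Section 9.1 size one comparison, the two BMS-986165 groups pooled against placebo. Both state that 52 subjects in the pooled groups and "26 subjects in the placebo group will provide 88% power (at a one-sided significance level of 0.10"). Section 4.2 gives the numbers as "52 subjects in the combined BMS-986165 groups and 26 subjects in the placebo group", and Section 4.1 gives the allocation as 1:1:1 over three arms, so the pooled comparison is 2:1. In the public copy the power sentence breaks off after the significance level in both places. No effect size or standard deviation can be read, which is consistent with redaction.

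Section 9.4.1 then does two things with the primary endpoint. For estimation, it gives relative differences "on the original scale based on least-square means and the corresponding 2-sided 95% CIs will be provided for combined BMS-986165 treatment groups and placebo". For inference, it says: "For statistical testing, comparison of the combined BMS-986165 treatment group compared to placebo will be performed". It does not repeat the level or sidedness of that test, names no interval other than the 95% one, and makes no Type 1 error adjustment. Section 9.4 leaves complete analysis details to an SAP that is to be final before database lock.

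**The concern.** A two-sided 95% interval excludes no effect, in the favourable direction, exactly when the one-sided p-value is below 0.025. The sizing accepts p-values up to 0.10. Between those limits the test is positive and the printed interval crosses no effect, and Section 9.4.1 does not say in so many words which of the two decides.

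The stakes would be real if the plan left this open. Section 9.6.5 says that the Week 24 analyses feed the planning of later development. A result in the band between the two levels could be called a success or a failure, and a choice made after unblinding would be post hoc. A reader who looked only at the interval might also credit it with the 88% power that belongs to the test.

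**Working it through.** **Inputs.** Pooled active n = 52 and placebo n = 26 (Sections 4.2 and 9.1). Power 88% at one-sided 0.10 (Section 9.1 and synopsis). Interval two-sided 95% (Section 9.4.1 and synopsis).

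**The plan's own figure.** The 88% cannot be reproduced independently, because the effect size and standard deviation are not visible. It can be inverted, since power and level together fix the noncentrality:

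- Noncentrality = z(0.90) + z(0.88) = 1.2816 + 1.1750 ≈ 2.457
- Standard error in SD units = √(1/52 + 1/26) = 0.240
- Implied standardized effect = 2.457 × 0.240 = 0.590 SD

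Putting 0.590 SD back in at one-sided 0.10 returns 88.0%, but only by construction.

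**Power if the 95% interval were the criterion.**

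- Normal approximation: Φ(2.457 − 1.960) = Φ(0.497) = 69.0%
- Noncentral t with 72 degrees of freedom: 68.4%

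**How often test and interval part company.**

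| Situation | Test positive | 95% CI excludes no effect | Test positive, CI includes no effect |
|---|---|---|---|
| Effect assumed in the sizing is true | 88.0% | 69.0% | 88.0 − 69.0 = 19.0% of all trials |
| No effect | 10.0% | 2.5% | 10.0 − 2.5 = 7.5% of all trials |

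In the first row, the share among trials with a positive test is 19.0/88.0 = 21.6% (22.3% with the t distribution). A simulation of 2,000,000 draws gave 88.1%, 69.1%, 19.0% and 21.5%. If the stated 88% is rounded from anywhere between 87.5% and 88.5%, the 69% moves only between 68.2% and 69.9%, and the share of positive trials between 22.1% and 21.0%.

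**What an added 80% interval would bring.** A two-sided 80% interval excludes no effect exactly when the one-sided 0.10 test is positive, so it has the same 88.0% power and repeats the test's verdict. It can also be recovered from what is already planned: on the log scale its half-width is about 1.2816/1.9600 = 0.65 of the 95% half-width around the same estimate.

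**Which rule the text supports.** Section 9.1 attaches one-sided 0.10 to combined active against placebo. Section 9.4.1 names that same comparison as the one tested. No other level is attached to it. The intervals are only said to be provided, and nowhere are they tied to a claim of success.

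**The case for a change.** The strongest case for a change is that level, sidedness and success rule belong in the primary analysis section, and Section 9.4.1 has none of them. The 95% interval is never labelled as descriptive. The visible text has no SAP passage that settles the matter, and deferring to a later document is weaker than stating the rule. Section 6.7 lets the sponsor end access to study treatment for failure to meet study objectives, yet no section defines meeting the efficacy objective in numbers. A band holding about one in five positive trials is not a rarity.

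The arithmetic stands, and so does the observation that Section 9.4.1 leaves the level out. What does not stand is the step from there to two competing rules. The 88% does not fall to 69%, because the planned test is still carried out at the level it was sized for. The 69% applies only to a criterion that the plan never adopts. The band itself is no defect either, since any test run above one-sided 0.025 and shown with a 95% interval has one. The worry that readers will credit the interval with 88% power is weak, because the power statement carries its own level in the same clause.

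**Conclusion.** No change follows. The plan sizes and tests one pooled comparison at one-sided 0.10 with 88% power and describes the effect with a conventional 95% interval. In a phase 2 trial whose Week 24 results guide further development, that is a fair trade-off: a lenient test for the go-forward question, and a stricter interval so that uncertainty is not understated. Powering the 95% interval itself at 88% for the same effect would take 43 + 86 = 129 subjects instead of 78.

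The missing level in Section 9.4.1 is a matter of cross-reference. An analyst following the document takes it from Section 9.1 or the synopsis, where it is the only level given for this comparison. An 80% interval or a note on the 69% figure would be presentation and would alter neither the estimate nor the test result.

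The figures (about 69% power for the interval; 19% of all trials and about 22% of positive ones in the band) assume that the stated 88% is correct, that the effect behind it is true, that all 78 subjects contribute, and that the estimate is approximately normal on the log scale. They do not depend on the effect size that is missing from the public copy. The conclusion would differ only if some text made the 95% interval the success criterion, and none in the visible document does.

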## 9.2 Populations for Analyses

The analysis populations are defined as follows:

Population	Description
Full Analysis Set for Part B	All randomized subjects at the beginning of Part B; following the intent-to-treat principle, subjects will be analyzed according to the treatment assigned at randomization at the beginning of Part B
As-treated Set for Part B	
All randomized subjects who took at least one dose of blinded study treatment at the beginning of Part B; this population will be used for the safety analyses for Part B. Data in this data set will be analyzed based on randomized treatment for Part B, except in the following cases:
 
 
• If a participant received the same incorrect treatment throughout the study, then the participant will be analyzed based on the treatment received
 
• If a participant received study treatment from more than one treatment group, and none of the administrations were consistent with the assigned randomized treatment group, then the participant will be analyzed based on the first treatment received
 

MMF	All subjects who take open-label MMF treatment

## 9.3 Endpoints

### 9.3.1 Primary Efficacy Endpoint

[figure not shown]
Percentage change from baseline in 24-hour UPCR at Week 24

[figure not shown]
### 9.3.2 Primary Safety Endpoint

Adverse events, vital signs, ECGs, and laboratory abnormalities from baseline through Week 52

### 9.3.3 Secondary Efficacy Endpoints

- PRR at Week 24, defined as  $\geq 50\%$  reduction from baseline in 24-hour UPCR
- Complete renal response (CRR) at Week 24, defined as both of the following:
  - 24-hour UPCR  $\leq 0.5$  mg/mg
  - eGFR (using the MDRD equation)  $\geq 60$  mL/min or  $\leq 20\%$  decrease from baseline
- CRR at Week 52
- CRR + successful corticosteroid taper to  $\leq 7.5$  mg/day at Week 24
- CRR + successful corticosteroid taper to  $\leq 7.5$  mg/day at Week 52
- PRR at Week 52

## 9.4 Efficacy Analyses

Categorical data will be summarized as frequency counts and percentages. Continuous data will be summarized using n, mean, standard deviation, median, minimum, and maximum unless otherwise specified. Efficacy variables will be summarized for all visits in which the variable is assessed. Complete details of the planned analyses will be documented in the Statistical Analysis Plan (SAP) and finalized before database lock. Summaries will be provided for the Full Analysis Set (FAS) population by randomized treatment for Part B. 

Additionally, summaries will be provided for the MMF population for subjects continuing open-label treatment.

### 9.4.1 Primary Endpoint Analysis

The analysis of covariance (ANCOVA) for change from baseline in log-transformed 24-hour UPCR at Week 24 will be performed with treatment groups (BMS-986165 3 mg BID, BMS-986165 6 mg BID, and placebo) and randomization stratification factors (24-hour UPCR < 3.0 mg/mg versus  $\geq$  3.0 mg/mg, and total cumulative IV corticosteroid methylprednisolone < 250 mg versus  $\geq$  250 mg) as fixed effects with log-transformed baseline value added into the model as a covariate. Relative treatment differences in percentage change from baseline in 24-hour UPCR at Week 24 on the original scale based on least-square means and the corresponding 2-sided 95% CIs will be provided for combined BMS-986165 treatment groups and placebo. Additionally, least-square means and 2-sided 95% CIs will be provided for the relative difference between each BMS-986165 treatment group and placebo for the FAS.

Prior to unblinding the appropriateness of the log-transformation will be investigated. Further details will be provided in the SAP. For statistical testing, comparison of the combined BMS-986165 treatment group compared to placebo will be performed. There will be no adjustment of the Type 1 error rate for multiple comparisons or testing of multiple endpoints.

#### 9.4.1.1 Imputation Methods for Primary Endpoint

The Multiple Imputation (MI) method will be used for the analysis of primary endpoint at Week 24. The MI is used to impute the missing outcomes for BMS-986165 and placebo treated subjects at Week 24, who discontinued or who have missing values for other reasons at Week 24. The imputation model will have exactly the same baseline covariates as the ANCOVA model above. Multiple draws from the posterior predictive distribution estimates will be used for the imputation; each imputed dataset will be analyzed with ANCOVA model described above. The

PROC MIANALYZE procedure in SAS will be used to pool the ANCOVA results. It should be noted that 24-hour UPCR is collected for the first time postbaseline at Week 24 and not at earlier time points.

The efficacy assessment after the start of protocol-prohibited medication/therapy that could improve LN will be considered missing for the statistical analysis and will be imputed as described above.

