**Table 3: Procedures and Assessments in Part B of IM011073 (52-Week Blinded Treatment Period)**

[figure not shown]
Visit Number	B1	B2	B3	B4	B5	B6	B7	B8	B9	B10	B11	B12	B13	B14/ EOT a	B15 a	Notes
Study Week/Day	D1	W4 D29 ±3d	W8 D57 ±3d	W12 D85 ±3d	W16 D113 ±3d	W20 D141 ±3d	W24 D169 ±3d	W28 D197 ±3d	W32 D225 ±3d	W36 D253 ±3d	W40 D281 ±3d	W44 D309 ±3d	W48 D337 ±3d	W52 D365 ±3d	28-D FU ±3d	The final study visit (for noncontinuing subjects) will occur 28d±3d after the visit at W52
Laboratory tests and other procedures																
UA with microscopic examination		X	X	X	X	X	X	X	X	X	X	X	X	X	X	Clean-catch specimen; if the UA is positive for leukocytes, blood, or bacteria, a urine culture should be performed if appropriate
UPCR		X	X	X	X	X	X	X	X	X	X	X	X	X		First morning voided specimen; second morning void may be used if first morning void was not collected
24-hour urine for UPCR c							X and ±7d							X and ±7d		Two 24-hour urine specimens will be collected for Visits B7 and B14; one should be collected at the visit and one returned either before or after per site/subject preference. The subject must provide both samples within the total 14-day window.
Urine pregnancy test for WOCBP only	X	X	X	X	X	X	X	X	X	X	X	X	X	X	X	A negative result within 24 hours before dosing on D1 is required

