#### **9.4.2.1 Imputation Methods for Secondary [REDACTED] Endpoints**

Nonresponder imputation will be used for the secondary and exploratory binary endpoints, as applicable, for subjects who discontinue early, start a protocol-prohibited medication/therapy that could improve LN, or who have otherwise missing endpoint data at or prior to the specified endpoint.

For continuous secondary [REDACTED] efficacy endpoints that are only collected at one time point, the MI method as described for the primary endpoints will be applied to deal with missing data.

For continuous secondary [REDACTED] efficacy endpoints that are collected more frequently, an MMRM method with unstructured variance covariance matrix specified for the model will be used for handling the missing data.

The efficacy assessment after the start of protocol-prohibited medication/therapy that could improve LN will be considered missing for the statistical analysis and will be imputed as described above.

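### The primary-endpoint imputation uses only the ANCOVA's own baseline covariates, so it reproduces a complete-case ANCOVA and ignores the 4-weekly spot UPCR

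*Combined protocol and SAP*

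**What the plan says.** The primary ANCOVA of change in log 24-hour UPCR at Week 24 (protocol section 9.4.1) "will be performed with treatment groups (BMS-986165 3 mg BID, BMS-986165 6 mg BID, and placebo", together with the two stratification factors and log baseline 24-hour UPCR.

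Section 9.4.1.1 imputes Week 24 values that are missing through discontinuation or any other cause. Values obtained after the start of a prohibited treatment that could improve nephritis are also set to missing and imputed. On the imputation model it says: "The imputation model will have exactly the same baseline covariates as the ANCOVA model above". Each imputed data set goes through the same ANCOVA and the results are pooled. The section adds: "It should be noted that 24-hour UPCR is collected for the first time postbaseline at Week 24 and not at earlier time points". No post-baseline variable is named.

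A spot UPCR is nevertheless scheduled throughout Part B. The UPCR row of Table 3 is marked at every visit from Week 4 (B2) to Week 52 (B14), with the note "First morning voided specimen; second morning void may be used if first morning void was not collected". Section 8.7.3.2 repeats it for Parts A and B: "First morning voided urine specimens will be collected; the first morning void is preferred".

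For continuous secondary endpoints measured repeatedly, section 9.4.2.1 does draw on the repeated visits: "an MMRM method with unstructured variance covariance matrix specified for the model will be used for handling the missing data". Section 9.4.1.2 leaves sensitivity analyses for the primary endpoint optional, to be set in the SAP.

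**The concern.** Imputation recovers information only if its model contains something the analysis model lacks. Here the two models match, so a subject without a usable Week 24 value adds nothing. That subject is treated as an average completer with the same arm, strata and baseline.

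This is harmless if, given those variables, missingness is unrelated to the Week 24 value. That is doubtful here, because a subject may stop or start prohibited therapy because proteinuria is not falling. The subject's own spot UPCR may already show this, yet the model does not look at it. The bias can go either way. The drug effect is understated if failures leave more often on placebo, and overstated if they leave more often on drug. The result at stake is the primary efficacy estimate in a trial of 78 subjects.

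**Working it through.** **Inputs from the protocol.** Section 9.1: "A sample size of 52 randomized subjects in the combined BMS-986165 treatment groups" and "26 subjects in the placebo group will provide 88% power (at a one-sided significance level of 0.10". Section 9.4.1: ANCOVA with three treatment groups, two strata and log baseline. Table 3: spot UPCR at Weeks 4, 8, 12, 16 and 20 before the endpoint.

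**Assumptions (not in the documents).** Missing rate of 10 to 30%; correlation of spot with Week 24 24-hour UPCR mainly 0.6 to 0.8.

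**1. The stated 88%.** The public text gives no effect size or SD, so 88% cannot be checked independently. Solved backwards:

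d = (z₀.₉₀ + z₀.₈₈) × √(1/26 + 1/52) = (1.2816 + 1.1750) × 0.2402 = 0.590 SD

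Using the t distribution with 72 df gives 0.593 SD.

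**2. Why the imputation adds nothing.** Let o and m mark subjects with observed and missing outcomes, and let b be the complete-case estimate. With many imputations the imputed outcomes average X_m b. The pooled estimate is then

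(X′X)⁻¹(X_o′y_o + X_m′X_m b) = (X′X)⁻¹(X_o′X_o + X_m′X_m) b = b.

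Numerical check on one data set with 18 of 78 missing: complete-case −0.465 (SE 0.2455); imputation with the same covariates and 5,000 draws −0.463 (SE 0.2454). Over 1,500 simulated trials per scenario the mean estimates agreed within 0.001 and correlated 0.993 to 0.998.

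This takes treatment group to be in the imputation model. If it were left out, the estimate would shrink to about −0.37 against a true −0.472, even with 20% missing completely at random.

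**3. Size, first simulation.** Settings: 3,000 trials per case, 26 per arm, true effect −0.593 SD, 20% missing overall, 30 imputations, and stopping possible after any visit from Week 4 to Week 20. Correlations were 0.6 to 0.7 at Week 12 and 0.7 to 0.8 at Week 20. The comparison model adds spot UPCR at Weeks 4, 12 and 20. Pairs are low/high correlation. Bias is estimate/−0.593 − 1; for example, 0.554/0.593 = 0.934, so 7% too small. Monte Carlo SE is 0.005 on estimates and about 0.7 points on power.

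| Case | Planned | With spot UPCR | Power, planned → with spot |
|---|---|---|---|
| 1. Random | −0.594/−0.591 | −0.594/−0.590 | 80% → 82–83% |
| 2. Follows latest spot value, same rule in all arms | −0.554/−0.548 (7–8% too small) | −0.587/−0.584 (1–2%) | 77% → 81–82% |
| 3. Follows unobserved true proteinuria | −0.545/−0.552 (7–8% too small) | −0.574/−0.589 (1–3%) | not reported |
| 4. Extreme: failures stop on placebo only | −0.476/−0.459 (20–23% too small) | −0.573/−0.574 (3%) | 64–66% → 81–82% |
| 5. Extreme: failures stop on drug only | −0.689/−0.718 (16–21% too large) | −0.609/−0.614 (3–4%) | see below |

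In case 5 with no true effect, the one-sided error is 19 to 22% planned and 11 to 12% with spot UPCR, against a nominal 10%. In case 2 the planned bias is 3 to 5% at 10% missing and 9 to 10% at 30% missing.

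**4. Second simulation.** Residual log SD 0.8, true difference 0.590 × 0.8 = 0.472, one interim spot value, about 22% missing driven by that value.

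- Correlation 0.8: planned −0.419 (1 − 0.419/0.472 = 11% too small), power 73.3%. With spot UPCR −0.470, power 82.6%.
- Correlation 0.6: planned −0.429 (9% too small), power 74.1%. With spot UPCR −0.467 (1% too small), power 80.4%.
- 20% missing completely at random: power 78.9 to 80.6% planned, 81.3 to 84.7% with spot UPCR.

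**5. Third simulation and weaker correlations.** With about 20% missing, spot-driven stopping and correlations of 0.6 to 0.8, the planned effect was 9 to 10% too small with power of 76 to 77%. With spot UPCR there was almost no bias and power was 84 to 85%. At correlations of 0.3 to 0.4 the bias fell from about 6% to 1%. A simpler check with 16 to 18% missing and correlations of 0.3 to 0.5 put the planned bias at only 1 to 2%.

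**The case against.** The strongest reply is that the sentence fixes the baseline covariates without expressly ruling out post-baseline ones, and that section 9.4 leaves full detail to the SAP. No separate SAP text is among the documents, so a later one could add spot UPCR. That limits how sure one can be about what will be done. It does not repair the rule as written: no auxiliary is named, and the remark about 24-hour UPCR suggests none was intended.

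The second reply is about size. In cases 1 to 3 the bias is at most 8%. That is 0.08 × 0.593 = 0.05 SD against a standard error of about 0.28, so under one-fifth of a standard error. The large figures come from one-arm stopping, which nothing in the documents supports. Correlations could also be lower than 0.6, since section 6.6.1 allows a corticosteroid burst in the first 8 weeks and tapering up to Week 20. Missingness may be below 20%, because a Table 3 note keeps randomised subjects who stop early in follow-up unless they withdraw consent. All of this stands as a limit on size. It does not favour the planned model, since adding spot UPCR did no harm at low correlations.

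Two smaller points also stand. The plan is consistent with its own rule, because section 9.4.2.1 applies the same imputation to continuous secondary endpoints measured once. And the Week 24 spot value could help for subjects who attend but lack a valid 24-hour collection.

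**Conclusion.** The concern holds. As written, the primary imputation is a complete-case ANCOVA up to Monte Carlo error, provided treatment group is in the model; if it is not, the result is worse. This follows from algebra and was confirmed numerically.

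The size depends on a missing rate and a correlation that the documents do not give. With about 20% missing and the same spot-driven stopping rule in every arm, expect an effect 7 to 11% too small and 4 to 9 power points lost relative to a model with spot UPCR, at correlations of 0.6 to 0.8. At correlations of 0.3 to 0.5 the bias is 1 to 6%. If missingness is purely random there is no bias and the loss is 2 to 4 power points. Larger errors, including a one-sided error near 20%, need failure-driven stopping confined to one arm. This should be fixed before database lock.

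**What to change.** Replace the covariate sentence in section 9.4.1.1 with:

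> Missing log 24-hour UPCR at Week 24 will be imputed from one model fitted across arms, containing randomised treatment group, both stratification factors, log baseline 24-hour UPCR, and log first-morning-void UPCR at Weeks 4, 12 and 20 of Part B. Spot values after the start of prohibited therapy are excluded, and missing spot values are imputed in the same procedure.

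The endpoint and the analysis ANCOVA stay as they are. The Week 24 spot value may be added as a refinement.

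The cost is wording and a little programming, with no new data. The model gains three parameters with 78 subjects. Using all five spot visits gained at most about 1 power point over three in cases 1 to 3 and about 2 in case 4, so the short list is enough. The new model still assumes data are missing at random, so it does not replace a missing-not-at-random sensitivity analysis, which section 9.4.1.2 should make firm.
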